**Study questions:****Primary:**

Do the mean outcomes for these 3 age groups differ (as they are, unadjusted, and using JA 'as prescribed' by the Swedish national Board of Health and Welfare (Socialstyrelsen)?

To what extent does adherence and other covariates explain the potential differences in outcomes?

**Secondary:**

Does the adherence to JA treatment differ across age groups?

Does the JA uptake differ by age when comparing age distribution of JA participants with age distribution of OA in the Skåne population?

---

**Background**

Osteoarthritis (OA) is among the leading causes of disability worldwide and due to its rising prevalence, the identification of appropriate care and care delivery modalities is a priority for the health care systems. Exercise and education constitute the first-line intervention for people with knee and hip OA and are effective regardless of symptoms and disease severity. This first-line intervention is available as face-to-face programs, or digital programs via eHealth apps. No published studies have yet examined if, among the OA population, the uptake, or the outcomes of the program, differ between younger or older participants in a digital first-line OA intervention. Our understanding of how background (demographic) factors interact with uptake and outcomes is incomplete.

**Methods**

This is an observational, retrospective register-based study of participants in a digital osteoarthritis self-management program.

All participants signed informed consent digitally upon registration. The regional ethics committee of Lund University and the Swedish Ethical Review Authority provided ethical approval (Dnr: 2018/650, 2019-02232 and 2020-05431). The study adheres to the STROBE guidelines for observational studies.

**Setting and participants**

Participants joined the digital OA self-management and education program (see Intervention below for details), through recommendation by their local orthopaedic surgeon or physiotherapist, and via online advertisements and campaigns placed on search engines and social networks. Included participants had a radiographic and or clinical diagnosis of hip or knee OA from a physical therapist or physician (95% of all patients at the date of data extraction). Individuals without a prior diagnosis had clinical OA confirmed by an orthopaedic surgeon or physiotherapist via telephone (diagnosis according to NICE UK criteria and Swedish National Guidelines, and confirming the absence of any red flag symptoms), or if deemed necessary were recommended to seek face-to-face care before inclusion in the program.

All data for the present study were extracted from the digital self-management program data registry on the 22nd of March 2021. Criteria for inclusion in the primary data extraction were:

- Having registered in the program and had the first telephone contact with the physiotherapist assigned to the patient, and enrolled between March 1, 2018 and November 30, 2020.
- Having reported hip or knee as most symptomatic (index) joint
- Having provided 3-month follow-up data on or before February 28, 2021

These selection criteria resulted in 14006 eligible participants.

Adherence was defined as the percentage of completed activities (exercises, and text or video lessons on OA, with quizzes on lesson material) per the pre-defined period of 12 weeks. A cut-off of 80% or higher adherence corresponds to the National Recommendations for first-line knee and hip OA treatment by the Swedish National Board of Health and Welfare (1).

#### *Intervention*

The intervention consisted of a digital, structured and individualized first-line treatment program for people with hip or knee OA (Joint Academy®; [www.jointacademy.com](http://www.jointacademy.com) ). The physiotherapist-led program consists of instructions for neuromuscular exercises appropriately adjusted to each patient in regard to degrees of complexity and difficulty. Exercises are distributed daily during the whole participation period, in general two per day, for a total of 163 exercise sessions over 12 weeks. While rating perceived difficulty and adding comments, patients also indicate when exercises are completed. Program progression is halted until all exercises for the day are marked as completed. Information (based on current national OA management guidelines and research) in the form of text or video lessons (with quizzes on the material after each episode) on subjects related to OA, OA symptoms and management is also distributed to each participant. The lessons come packed in themes, with each theme containing 1–5 lessons where participants receive one theme per week the first six weeks, and then every other week, for a total of 31 lessons over 12 weeks. Completion of a lesson is indicated by the patient answering the quiz correctly. Additionally, continuous access to, and dialogue with, is provided by a physiotherapist through an encrypted chat function and telephone.

### **Main exposure & outcomes**

#### *Exposure*

Age (categorized in 3 groups) is the main exposure of the interest.

#### *Outcomes*

*For research question 1:*

1. Joint pain will be assessed at baseline and at week 12 using the Numerical Rating Scale (NRS, discrete boxes 0–10) with the instruction: “Mark on this scale how much pain you had the last week in your hip/knee”, followed by a 0–10 scale where 0 was defined as No pain and 10 was defined as Maximum pain.

2. As a measure of physical function, the 30 second chair rise will be measured at baseline and week 12, performed by the participant with the help of an instruction video with a coupled visual timer. The patient enters the performed number of repetitions after each test.
3. Among other outcomes to be reported are changes between baseline and 12 weeks follow-up in self-reported KOOS-12 and HOOS-12, KOOS-PS, HOOS-PS, response to anchor questions, response to questions on satisfaction or not with treatment, fear of movement, and walking difficulties-(Table 1).

All outcomes will be self-assessed and self-entered using the digital program interface and selected based on the International Consortium for Health Outcomes Measurement Standard Set for Hip & Knee Osteoarthritis (ICHOM) (2).

*For research question 2:*

Adherence as measured (between 0 to 100%) and desirable adherence  $\geq 80\%$  (i.e.  $\geq 80\%$  completed exercises, text or video lessons on OA, with quizzes on lesson material offered in the digital program) between 0 and 12 weeks of first-line OA treatment delivered digitally.

*For research question 3:*

Registration in JA is the outcome of interest.

## **Endpoints**

*Main endpoints*

- a) Self-reported change in index joint (knee or hip) pain on the NRS-scale between baseline and 12 weeks of follow-up for the three age groups  $\leq 59$ , 60-69, and  $\geq 70$
- b) Self-reported change between baseline and 12 weeks in 30-second chair rise test for the three age groups  $\leq 59$ , 60-69, and  $\geq 70$

*Other endpoints*

Outcomes will be compared for the three age groups  $\geq 59$ , 60-69, and  $\geq 70$  for the following

KOOS-12 questionnaire

HOOS-12 questionnaire

KOOS-PS questionnaire

HOOS-PS questionnaire

Physical activity

Responder criteria and patient responses to questions on satisfactory health state and treatment failure.

## **Covariates**

We will examine to what extent the potential differences across age groups in research questions 1 & 2 can be explained by the baseline demographic, socioeconomic (employment status and education level) and clinical (BMI, co-morbidity, overall health status, index joint) characteristics.

## **Sample size**

This being a registry-based study of prospectively collected data, no formal power calculation will be provided. However, with the number of patients providing data, statistical power will be more than sufficient to analyze conclusively relevant group differences for the main endpoints.

## **Statistical analysis**

### **Data description**

Summary data by age groups will be described by the mean value, standard deviation and number of observations or the number and percent of the categories of interest.

For research question 1, we perform ordinary least squares (OLS) regressions of the outcome of interest on age group and the baseline value of that outcome. Next, we adjust for all other covariates including adherence. Finally, we will employ the Oaxaca-Blinder (OB) decomposition technique to understand the reasons for potential differences across age groups in the outcome of interest. OB decomposition decomposes differences between groups into “explained” and “unexplained” portions. The explained part estimates the amount of the differences in the outcome attributable to age group differences in the means of explanatory variables. The unexplained part originates from the differences in the associations between the outcome and explanatory variables across age groups. This latter part represents the magnitude of difference which will remain even if the age groups had identical means of covariates. In addition to decomposition of mean differences between age groups, we will also decompose the difference in variance of the outcome using OB technique. In interpreting the findings, we will take into account the minimal clinically important difference for each outcome (e.g. differences above 10 (scale 0-100), or 1 (scale 0-10) in pain).

For research question 2, we will use OLS regression (with adherence as measured) and logistic regression (for desirable adherence: adherence $\geq$ 80%) to investigate age group differences in these outcomes.

Similar to research question 1, we will use OB technique to decompose the potential gap between age groups in these two outcomes. In interpreting the findings, we will take into account the minimal clinically important difference of 2.0 in repetitions”

For research question 3, we will obtain data on doctor-diagnosed knee and/or hip OA among the Skåne population by age group and contrast this with the JA participants resident in the Skåne. This comparison will reflect what proportion of people with doctor-diagnosed OA in each age group registered in JA.

In all studies we will conduct subgroup analyses by index joint (knee & hip) if data allows. Moreover, since the rate of dropout between the baseline and 3 months follow up might be different across age groups, we will apply inverse probability weighting to account for this.

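### The first primary question asks for the unadjusted age difference and the main endpoints are changes, but both regressions for research question 1 condition on baseline and the modelled outcome is not defined

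*Protocol*

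**What the plan says.** Four parts of the Protocol bear on this.

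- **Study questions, Primary.** The first question is "Do the mean outcomes for these 3 age groups differ (as they are, unadjusted". The second is separate: "To what extent does adherence and other covariates explain the potential differences in outcomes".
- **Endpoints, Main endpoints.** Both are changes over the program: "Self-reported change in index joint (knee or hip) pain on the NRS-scale between baseline and 12 weeks of follow-up", and "Self-reported change between baseline and 12 weeks in 30-second chair rise test for the three age groups".
- **Statistical analysis, Data description.** The first model for research question 1 is given by "we perform ordinary least squares (OLS) regressions of the outcome of interest on age group and the baseline value of that outcome". The second follows: "Next, we adjust for all other covariates including adherence". The third step is a decomposition: "OB decomposition decomposes differences between groups into “explained” and “unexplained” portions". Before any of these, "Summary data by age groups will be described by the mean value, standard deviation and number of observations".
- **Methods.** The study is observational and uses registry data, so nothing balances the age groups at baseline.

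The analysis section uses a generic term for the outcome. It does not say whether the dependent variable is the 12-week change or the week-12 value.

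**The concern.** The question, the endpoint and the model do not line up. The question is about the age groups as they stand. The endpoint is a change. The first model compares people of different ages who had the same starting value, and the second model conditions on still more.

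In a randomised comparison this would hardly matter, because expected baseline means are equal and both contrasts target the same quantity. Age groups are intact groups, and their baseline pain and chair-rise counts may well differ. The change contrast and the baseline-adjusted contrast then answer different questions (Lord's paradox). If the first regression is reported as the answer to the first primary question, part of any baseline gap will appear as an age difference in program outcome.

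**Working it through.** **The Protocol's own figure.** There is none to reproduce. The Protocol reports no baseline means by age, no slope and no standard deviation, and the Sample size section gives no power calculation.

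**Three contrasts.** For two age groups, let D be the difference in mean change, dB the difference in baseline means, and b the pooled within-group slope of the week-12 value on baseline.

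- Change, age group only: D
- Week-12 value, age group only: D + dB
- Either outcome, with baseline in the model: (D + dB) - b × dB = D + (1 - b) × dB

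The third line is the same whether the dependent variable is the change or the week-12 value. Defining the outcome therefore does not by itself remove the mismatch. It does decide which raw gap (D or D + dB) the descriptive table and the decomposition refer to. The baseline-adjusted and change contrasts agree only if dB = 0 or b = 1.

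**Size of (1 - b) × dB.** All values of dB and b are assumptions.

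| Pain, baseline gap (0–10 scale) | b = 0.4 | b = 0.5 | b = 0.6 |
|---|---|---|---|
| 0.2 | 0.12 | 0.10 | 0.08 |
| 0.4 | 0.24 | 0.20 | 0.16 |
| 0.6 | 0.36 | 0.30 | 0.24 |

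| Chair rise, baseline gap (repetitions) | b = 0.7 | b = 0.8 | b = 0.9 |
|---|---|---|---|
| 1 | 0.3 | 0.2 | 0.1 |
| 2 | 0.6 | 0.4 | 0.2 |
| 3 | 0.9 | 0.6 | 0.3 |

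**Against the thresholds in Data description.** For pain the threshold is 1 point, so the largest entry is 36% of it. For chair rise, 0.9 / 2.0 = 45%. (The 2.0 figure stands in the text on research question 2, but its unit is repetitions, so I read it as the chair-rise threshold.) Wider assumptions still stay below both: pain with gaps 0.25 to 1.0 and b 0.3 to 0.7 gives at most 0.70; chair rise with gaps 1 to 3 and b 0.6 to 0.9 gives at most 1.20.

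**Against sampling error, pain.** Take 14006 participants (Setting and participants), an assumed equal split of about 4669 per group, and an assumed SD of 2.2. The standard error of a pairwise difference is 2.2 × sqrt(2/4669) = 0.0455. The discrepancy is then 0.08/0.0455 = 1.8 to 0.36/0.0455 = 7.9 standard errors. I give no such ratio for chair rise in the range above, because Table 1 shows no count for that test.

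**Simulation check.** N = 14006, three roughly equal groups, and the same true mean change in every group; contrast is oldest minus youngest.

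| Setting (assumed) | Change, age only | With baseline | (1 - b) × dB | Week-12 value, age only |
|---|---|---|---|---|
| Pain: dB = 0.5, b = 0.5, SD 2.0 | 0.02 (SE 0.04) | 0.28 (SE 0.04) | 0.25 | 0.53 (SE 0.04) |
| Chair rise: dB = -2, b = 0.75, SD 4.5 | -0.02 (SE 0.07) | -0.50 (SE 0.06) | -0.50 | -1.93 (SE 0.09) |

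Groups with identical mean change show a clear age coefficient once baseline is in the model. The last column shows why the undefined outcome matters: the raw gap on the week-12 value is a different quantity again.

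**The case against.** **An unadjusted result is already in the plan.** This largely stands. Mean, SD and count per age group are enough to compute an unweighted pairwise difference and interval for any outcome so summarised. The total gap that Oaxaca-Blinder splits is itself a raw mean difference. A reader might infer from the two regressions that no unadjusted comparison will exist; the Protocol does not support that. What remains is that neither quantity is named as the answer to the first question, and neither is tied to the change endpoint.

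**Unadjusted may mean not adjusted for the listed covariates.** The Covariates section covers demographic, socioeconomic and clinical characteristics and does not name the baseline value of the outcome. The age-plus-baseline model could then be what the authors mean by unadjusted. This reading is possible, but the second step speaks of all *other* covariates, which implies that baseline already counts as one. At best the text is ambiguous.

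**Baseline adjustment is legitimate.** Agreed. A reader might infer that the adjusted model is biased and should go. Lord's paradox shows only that the two contrasts answer different questions. Error in a single self-entered baseline lowers b and so enlarges the discrepancy, but the same error enters the change score too, so it is no argument against one model alone.

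**Details belong in an SAP.** Confidence intervals and exact model form may be in an SAP not available here, and their absence is not the point. The Protocol itself fixes a first model that does not match its first question.

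**Conclusion.** The mismatch is real and should be fixed, as a matter of what the estimate means. The three textual premises are plain in the Protocol, and the algebra holds whenever baseline means differ and the slope is not 1. The size is not known from the Protocol. Under the assumed gaps, slopes and SD it is 0.08 to 0.36 pain points (about 1.8 to 8 standard errors with 14006 split equally) and 0.1 to 0.9 repetitions.

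A reader might infer that the headline conclusion could be reversed. The documents do not support that. All the amounts computed are below the Protocol's thresholds of 1 point and 2.0 repetitions, the Protocol says it will interpret findings against such thresholds, and the analysis section states no significance rule. A change of sign would need a true difference in change that is smaller than these amounts and in the opposite direction. The risk is that a small difference is mislabelled, or appears or disappears as statistically significant.

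**What to change.** In the Data description text for research question 1:

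1. State that the outcome for the main endpoints is the change from baseline to 12 weeks.
2. Add as step 1 an OLS model of that change on age group only, with pairwise differences and 95% confidence intervals, and name it as the answer to the unadjusted question. Make it consistent with the total gap decomposed by Oaxaca-Blinder, using the same outcome, participants and weights.
3. Keep the age-plus-baseline model as step 2, labelled as comparing people of different ages with equal starting values. The covariate and adherence model follows as now.
4. Show baseline means by age group beside both contrasts, so that a reader can see where any discrepancy comes from.

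The cost is one extra regression per endpoint and a few sentences of text. No new data are needed.

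### Research question 2 compares adherence by age only in people who returned 3-month data, although adherence is recorded without those data

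*Protocol*

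**What the plan says.** The first secondary question in the Protocol (Study questions) is "Does the adherence to JA treatment differ across age groups". It is not limited to people who reported at 3 months. The Outcomes section calls it research question 2 and measures adherence both as a percentage and as reaching 80% or more, "between 0 and 12 weeks of first-line OA treatment delivered digitally".

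Under Setting and participants:
- The source is a single extraction, dated 22 March 2021: "All data for the present study were extracted from the digital self-management program data registry".
- One inclusion criterion is "Having provided 3-month follow-up data on or before February 28, 2021".
- The resulting count is stated directly after the list: "These selection criteria resulted in 14006 eligible participants".
- The outcome of this question, taken over 12 weeks, is explained there too: "Adherence was defined as the percentage of completed activities".

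The Intervention section says that patients mark exercises as done in the program and that a lesson counts as completed once its quiz is answered correctly.

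Under Statistical analysis the plan reads "For research question 2, we will use OLS regression (with adherence as measured) and logistic regression", the latter for the 80% threshold, followed by an Oaxaca-Blinder decomposition. No other population is named for this question. The closing paragraph of that section plans inverse probability weighting, "since the rate of dropout between the baseline and 3 months follow up might be different across age groups".

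**The concern.** The set is selected on an event that happens at or after the end of the outcome window. People who stop doing the exercises are plausibly less likely to answer the 3-month questionnaire. The program also holds back further progression until the day's exercises are marked as done, so poor adherers stall. If return depends on adherence and the return rate also differs by age, which the protocol itself allows for, the age comparison among returners is not the comparison among people who started.

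At stake are the mean contrast, the odds ratio and their decomposition. Adherence levels are also likely to be overstated in every age group. A large sample does not help: it gives a narrow interval around a value that may be wrong.

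**Working it through.** **Is the restriction needed?** The adherence denominator is 163 exercise sessions + 31 lessons = 194 activities (Intervention), and 80% of that is 155.2. None of these is a 3-month questionnaire item. Table 1 shows 14006 participants in total and 14006 with 3-month joint pain, which confirms that the described set holds returners only.

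**When is the odds ratio biased?** Let p be the true proportion with adherence of at least 80%, and let rH and rL be the return rates at or above and below 80%. Among returners

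P(adherent | returned) = p·rH / [p·rH + (1−p)·rL],

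so the odds are multiplied by rH/rL. The odds ratio is therefore unaffected only if rH/rL is the same in each age group.

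Assumed example: true 50% (younger) versus 60% (older), odds ratio 1.50. Return is 90%/30% (adherent/non-adherent) in the younger and 90%/60% in the older group.
- Younger: 0.45/(0.45 + 0.15) = 75.0%.
- Older: 0.54/(0.54 + 0.24) = 69.2%.
- Observed odds ratio: 1.50 × (0.9/0.6)/(0.9/0.3) = 0.75, so the direction reverses.

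If return is 90%/60% in both groups, the result is 60.0% versus 69.2%. The odds ratio stays at 1.50, but both levels are overstated.

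**How large could it be with no true age difference?** All inputs are assumptions. Adherence A = 100·Beta(1.2, 0.8) in both groups (mean 60, 31.7% at 80 or more). Return follows logit P(return) = c + s·A, with the same s in both groups and c set to give the stated return rate. Results are by numerical integration; the shift is the mean in the higher-return group minus that in the lower-return group.

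| Return rates | s | Adherence gap, returners minus non-returners | Shift in mean contrast | Odds ratio (true 1.00) |
|---|---|---|---|---|
| 63% v 78% | 0.01 | 8.0 / 8.1 | −1.17 | 0.937 |
| 63% v 78% | 0.02 | 15.6 / 16.0 | −2.25 | 0.883 |
| 63% v 78% | 0.03 | 22.3 / 23.1 | −3.18 | 0.839 |
| 63% v 78% | 0.045 | 30.4 / 31.7 | −4.27 | 0.786 |
| 70% v 75% | 0.01 | about 8 | −0.39 | 0.978 |
| 70% v 75% | 0.045 | about 31 | −1.44 | 0.924 |
| 63% v 63% | any | equal | 0 | 1.000 |

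Check at s = 0.045, 63% v 78%: rH/rL is 1.74 and 1.37, and 1.37/1.74 = 0.79, as in the table. The returner means there are 71.2 and 67.0 against a true 60.

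For scale, with 14006 in equal thirds (assumed), n = 14006/3 ≈ 4669 per group. The 95% half-width of a difference in proportions near 50% is 1.96·√(2·0.25/4669) ≈ 2.0 percentage points.

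**Does the weighting repair it?** Weights on age group alone are constant within a group, so they leave the unadjusted contrast unchanged. For weights on age plus one baseline covariate, two scenarios were simulated with 400000 people per run, a true contrast of 0 and return of about 63% v 78%.

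| Return depends on | Latent correlation of covariate with adherence | Unweighted | Age + covariate weights |
|---|---|---|---|
| adherence (s = 0.045) and age | 0.1 / 0.3 / 0.5 | −4.39 / −4.41 / −4.16 | −4.36 / −4.18 / −3.46 |
| covariate and age only | 0.3 / 0.5 / 0.7 | −1.22 / −1.92 / −2.77 | 0.01 / −0.01 / 0.09 |

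In the first scenario, weights on age plus adherence itself bring the shift to between −0.15 and 0.13. Baseline weights therefore work when return is unrelated to adherence given the covariates, and do little otherwise. Any weight model also needs data on non-returners, whom the described extraction excludes.

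**The case against.** The protocol does not explicitly assign a population to research question 2. The follow-up criterion is attached to what it calls the primary extraction, and the weighting cannot be fitted without non-returners, so wider registry data may have been expected. This is fair as far as it goes. But the protocol says that all study data come from the registry extraction it describes and describes no other for this question, so the rule as written applies.

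The plan does anticipate age-related dropout, and weights that include adherence would largely remove the bias in the simulation. That needs the activity records of non-returners, and the same records allow direct analysis with no weighting.

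The magnitudes rest wholly on assumptions and are not a bound. The steepest case, s = 0.045, has return rising from 12% at zero adherence to 92% at full adherence in one group. The zero shift at equal return rates depends on equal slopes: with 70% return in both groups and slopes of 0.01 and 0.03, the returner means are 62.4 and 66.8, a shift of 4.4 points. The protocol gives no relevance threshold for adherence against which to judge these figures. All of this stands, and it is why no size is claimed.

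Using one set for research questions 1 and 2 also keeps the adherence gap consistent with the one that enters the outcome decomposition. That is a reason to report the responder analysis as well, not to let it alone answer a question about everyone who started.

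**Conclusion.** The concern holds. As written, research question 2 would describe adherence by age among people who stayed to report at 3 months, not among those who started the program. The restriction is unnecessary for an outcome recorded in the program. The bias is plausible rather than proven, and its size and direction cannot be derived from the protocol, which gives no return rates. Under the assumptions shown it ranges from nothing to about 4 points in the mean contrast and from 1.00 to 0.79 in the odds ratio, and it can be larger or reverse sign if the link between return and adherence differs by age. The question is secondary, so this is a change that should be made rather than a fatal flaw. Confidence is medium.

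**What to change.** Run the linear, logistic and decomposition analyses of research question 2 in everyone with an index hip or knee who registered, had the first physiotherapist contact and enrolled from 1 March 2018 to 30 November 2020, whether or not they returned 3-month data, using the program's activity records. Keep the weighted analysis of the 14006 as a sensitivity analysis; it also preserves the link to research question 1, which stays in responders. Report return rates by age group.

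If activity records of non-returners are not available, restate the question as adherence among 3-month responders and still report the return rates.

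The cost is one further registry query, assuming that activity records and baseline covariates of non-returners are kept. If the 12 weeks run from enrolment (not stated), the last window closed on 30 November 2020 + 84 days = 22 February 2021, 28 days before the extraction on 22 March 2021, so follow-up of activity would be complete. Reported adherence is likely to be lower than in responders.

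### Research question 3 promises the proportion of doctor-diagnosed people who registered, but the data described give a ratio of two counts not shown to be nested, and may count only people with 3-month data

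*Protocol*

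**What the plan says.** The secondary study questions in the protocol pose question 3 as a comparison of two age distributions: JA participants against people with osteoarthritis (OA) in Skåne. The Outcomes section fixes the outcome: "Registration in JA is the outcome of interest". The statistical section (under Data description) will obtain figures on doctor-diagnosed knee and/or hip OA in Skåne by age group and set them against JA participants living there. It interprets the contrast as follows: "This comparison will reflect what proportion of people with doctor-diagnosed OA in each age group registered in JA".

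Who counts as a JA participant is described only under Setting and participants. A list introduced by "Criteria for inclusion in the primary data extraction were" gives three conditions:

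- registration, a first call with the assigned physiotherapist, and entry within a fixed window ("enrolled between March 1, 2018 and November 30, 2020");
- an index joint that is either a knee or a hip, as named by the participant;
- a condition on follow-up, which is the one that matters here: "Having provided 3-month follow-up data on or before February 28, 2021".

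On the number of people who met all three, the section says: "These selection criteria resulted in 14006 eligible participants". Table 1 agrees with this: index-joint pain has 14006 entries at baseline and 14006 at 3 months.

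On diagnosis, the same section says that participants had a "diagnosis of hip or knee OA from a physical therapist or physician (95% of all patients at the date of data extraction". Those without a prior diagnosis had OA confirmed by telephone, by an orthopaedic surgeon or a physiotherapist. The last paragraph of the statistical section notes that dropout before 3 months may vary with age and plans inverse probability weighting for it.

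**The concern.** A proportion needs a numerator drawn from its denominator. Here the denominator is people with a doctor's diagnosis in Skåne. The JA side is limited only by residence, and its members may have been diagnosed by a physiotherapist or confirmed by telephone. No linkage to the diagnosis data is mentioned.

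Registration also happens at entry, whereas the only JA population described is selected on an event three months later. Counting that population would leave out people who registered and then left. Retention or diagnosis source that is the same at all ages cancels from an age comparison; if either varies with age it does not cancel. A difference in staying in the programme, or in who made the diagnosis, could then be reported as a difference in uptake, which is what question 3 asks about.

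**Working it through.** The protocol gives no figure for question 3, so there is nothing to reproduce. It gives no Skåne count, no retention rate and no share diagnosed by a doctor. The check is an identity, followed by illustrations with assumed values.

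**Notation, for age group a among Skåne residents**

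- D: people in the doctor-diagnosed OA data.
- R: all JA registrants.
- r: share of registrants with 3-month data (not given).
- f: share of registrants who are also in the doctor-diagnosed data (not given).

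**Level**

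- Quantity promised: u = f × R / D.
- All registrants counted: R / D = u / f.
- Only people with 3-month data counted, unweighted: r × R / D = (r / f) × u.
- Weighted by a correct 1/r: back to u / f. Weighting removes r but not f.

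With r and f each assumed between 0.5 and 1.0, r / f runs from 0.5 / 1.0 = 0.5 to 1.0 / 0.5 = 2.0. The two errors pull in opposite directions and can cancel (r = f = 0.7 gives 1.0).

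The one related figure in the protocol is the 95% with a prior diagnosis. It leaves 100% − 95% = 5% without one, or 0.05 × 14006 = 700 people. This assumes that a percentage stated for all patients at extraction applies to the 14006. If exactly 5% of all registrants lacked a doctor's diagnosis, R / D would be u / 0.95 = 1.05u. If none did, it would be 1.00u. If some physiotherapist-diagnosed participants also lacked one, the factor would be larger; no upper limit is given.

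**Age comparison**

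Apparent old/young ratio = true ratio × (r_old / r_young) × (f_young / f_old). The comparison of age distributions carries the same factors, because dividing one group's share among JA participants by its share among people with OA equals that group's count ratio divided by the overall one.

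With equal true uptake:

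| Assumed values | Apparent old/young ratio |
|---|---|
| r and f the same at all ages | 1.00 |
| equal f; r 0.80 young, 0.60 old | 0.60 / 0.80 = 0.75 |
| equal f; r 0.60 young, 0.80 old | 0.80 / 0.60 = 1.33 |
| equal r; f 0.9 young, 0.7 old | 0.9 / 0.7 = 1.29 |
| equal r; f 0.7 young, 0.9 old | 0.7 / 0.9 = 0.78 |
| r 0.60 and 0.80 with f 0.7 and 0.9 (young, old) | 1.33 × 0.78 = 1.04 |

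Equal retention is therefore not sufficient for a correct age pattern, since f may differ. It is not strictly necessary either, since the two factors can offset.

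**The case against.** The strongest defence is that the protocol never says question 3 uses the 14006. It names registration as the outcome, does not repeat the follow-up criterion when it describes the Skåne contrast, and calls its criteria those of a primary extraction. The weighting plan presupposes some data on people who dropped out. Its paragraph opens with wording that covers all the analyses, and adequate weighting would restore registrant numbers by age. The statistical analysis plan, not available here, may define the count. And the question as first posed, a comparison of age distributions, needs no linkage.

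Much of this stands. A reader might infer that question 3 will certainly count only people with 3-month data; the text does not establish that. Nor does it support saying that retention differences will go uncorrected, or that the age pattern is right only if retention is equal. But no wider set of registrants is described, the weighting is not tied to question 3, and no source of data on non-completers is named.

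A reader might also infer that some participants have no OA diagnosis, or that 5% is the share without a doctor's diagnosis. Neither follows. Everyone had a prior diagnosis or a telephone confirmation, some confirmations were by an orthopaedic surgeon, and some people diagnosed by a physiotherapist may have a doctor's diagnosis too.

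The defence does not reach the sentence that interprets the contrast. On any reading of the numerator, a ratio of two unlinked counts is there called a proportion.

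**Conclusion.** The point holds in two parts of different strength. First, without conditions: as described, the contrast does not give the proportion of doctor-diagnosed people who registered, because the JA count is not shown to be a subset of the doctor-diagnosed count. Second, conditionally: if the 14006 population is used without weighting, any age difference in 3-month retention enters the uptake comparison. Weighting could deal with this second part only. Separately, the age comparison is distorted if the share of registrants with a doctor's diagnosis varies by age.

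Size and direction cannot be derived from the protocol. The ranges of 0.75 to 1.33 for retention and 0.78 to 1.29 for diagnosis source rest wholly on assumed values, and no distortion at all is possible. The question is secondary and the repair is cheap, so the change should be made; the primary analyses are not affected.

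**What to change.** For question 3 only:

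1. Drop the 3-month follow-up criterion. Count all Skåne registrants with hip or knee as index joint in the enrolment window, 1 March 2018 to 30 November 2020, by age group.
2. State whether the first telephone contact is required, since the outcome is registration.
3. Set this count against doctor-diagnosed knee and/or hip OA in Skåne for a stated matching period, in the same age groups.
4. Report relative uptake by age: the age-specific ratio and the comparison of age distributions. State the difference in diagnosis source as a limitation, including that it may vary by age.
5. Keep the wording about a proportion only if individual records are linked. Restricting the JA side to participants who report a doctor's diagnosis would narrow the mismatch, but would not show that they are in the Skåne data.

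With all registrants counted, weighting is not needed for this question. The cost is one extra registry count, a stated period for a denominator that is to be obtained anyway, and a slightly weaker claim. Linkage would cost more and is optional.
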